# 6.9.2 Key Secondary Efficacy Analyses

The key secondary efficacy analysis is the change from Visit 3 to Visit 6 in Investigator CGI-S score.

The Key Secondary endpoint will be analyzed using Mixed-Effect Model for Repeated Measure (MMRM) for the ITT population. The model includes treatment, visit, and interaction between treatment and visit as fixed factors, and baseline as covariate. The model parameters will be estimated using restricted maximum likelihood method with unstructured variance-covariance matrix and Kenward-Roger approximation to estimate denominator degrees of freedom. The between-group comparison will be performed using the simple contrast at the respective visits. The least squares mean of 36 mg dose and placebo, the difference in the least squares mean (36 mg dose minus placebo), and the 2-sided 95% CI for the difference will be calculated.

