## 6.9.3 Additional Secondary Efficacy Analyses

- 1. Investigator CGI-I score at Visit 6
- 2. CHQ-28 score at Visit 6
- 3. PSI-4-SF scores at Visit 6 in:
  - a. Parental Distress
  - b. Parent-Child Dysfunctional Interaction
  - c. Difficult Child
- 4. Caregiver CGI-I score at Visit 6
- 5. SNAP-IV ADHD scores at Visit 6 in:
  - a. Inattention ratings
  - b. Hyperactivity/Impulsivity ratings
  - c. Oppositional Defiant Disorder
  - d. Combined Scale ratings
- 6. Percentage of responders with  $\geq$  50% reduction in the frequency of IA behaviors from baseline
- 7. Percentage of responders with  $\geq$  30% reduction in the frequency of IA behaviors from baseline

The other secondary endpoints will be analyzed using the ITT Population as follows:

Scores of CGI-I (investigator and caregiver) will be analyzed using a Mixed-Effect Model for Repeated Measure (MMRM) similar to the key secondary outcome.

CONFIDENTIAL Version 7.0

Scores for CHQ-PF28, PSI-4-SF, and SNAP-IV will be analyzed using the analysis of covariance method based on the ITT population. The model includes treatment and baseline as fixed independent covariates and Visit 6 value as a response variable. The least squares mean of each treatment group, the difference in the least squares mean (36 mg dose minus placebo), and the 2-sided 95% CI for the difference will be obtained.

The percentage of responders with at least 30% reduction and with at least 50% reduction in the frequency of IA behaviors per 7 days in the Treatment (Titration and Maintenance) period relative to the Baseline period will be derived analyzed using the logistic regression model with treatment as explanatory variables and baseline as covariate. Odds ratio (36 mg dose/placebo), and 95% CI for the odds ratio and p-value will be presented. In addition, the number and percentage of responders will also be tabulated.

If the null hypothesis for the primary analysis is not rejected, then no multiplicity adjustment will be done for the key secondary endpoint. If the key secondary endpoint hypothesis is rejected then, a sequential testing procedure to preserve the type I error rate at 0.05 will be conducted for the adiidtinal secondary endpoints as described below:

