6.5 Interim Analysis and Adaptive Design

There is no planned interim analysis.

6.6 *Timing of Final Analyses*

Data summary and statistical analysis will commence after all subjects have completed study Visit 7 (or discontinued prior to Visit 7) and the study database is cleaned and locked.

6.7 *Multicenter Study*

This is a multicenter study. The primary analysis will have all sites pooled. Where applicable, analysis adjusting for site effect or analysis evaluating homogeneity across sites may be carried out. If conducted, small sites (defined as those with sample size <9 ITT subjects/site) will be pooled with larger sites based on the geographic proximity.

6.8 *Multiple Comparisons/Multiplicity Adjustment*

Because of the early termination of the 18 mg arm based on the external data, there will be no formal hypothesis test and statistical comparison between the 18 mg arm and the placebo arm for any of the efficacy endpoints. Thus, there is no multiplicity adjustment due to the multiple dose arms to placebo comparisons with respect to the primary and key secondary endpoint analysis. Multiplicity adjustment for the multiple endpoints with respect to additional secondary end points will be carried out in a fixed sequential gate-keeping approach. The test of the null hypothesis of 36 mg vs placebo for additional secondary endpoints from one endpoint to the next endpoint will be carried out in such a way that the test of the subsequent endpoint will be conducted if and only if the test rejects the null hypothesis for the previous additional secondary endpoint. If any test fails to reject the null hypothesis with respect to a certain additional

secondary endpoint then there will be no test of hypothesis with respect to all subsequent additional secondary endpoints and these tests will all be considered failure.

6.9 *Examination of Subgroups*

In addition to the analysis adjusted for the confounding effects by the covariates (see Section 6.3), primary and key secondary efficacy variables will be summarized by subgroup to explore the heterogeneity of the treatment effect across subgroups. Subgroups are defined as follows:

- Gender (Male, Female)
- Age (6-9, 10-12)
- Race (White, Non-white)

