7.8.1 Primary Efficacy Analysis

The primary analysis will be based on the mITT population and the primary efficacy endpoint is percent change (PCH_T) in the frequency (unweighted score) of IA behaviors per 7 days in the treatment period relative to the Baseline period calculated over the number of days with non-missing IA diary. The analysis will be repeated for the ITT population, which follows the original primary efficacy analysis population definition.

Both of the above analyses will be performed using the Wilcoxon rank-sum test to compare the median SPN-810 36 mg with the median of the Placebo. The Hodges-Lehmann estimate of the difference (SPN-810 36 mg dose minus placebo) and the associated 95% confidence interval (CI) around the difference will be calculated. The statistical analysis will be presented in the table along with the summary of the change from baseline frequency (Table 14.2.1.1). The daily IA behavior diary will be listed. The daily frequency, the derived 7-day frequency for each week, and the derived 7-day frequency for the treatment period will be included (Listing 16.2.2.1.1 – Listing 16.2.2.1.2). Histogram of median percent change from baseline in the frequency of IA Behaviors in treatment will be created for 36 mg dose and Placebo (Figure 14.2.1.1).

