7.8.6 Analysis of Secondary Efficacy Endpoints

The analyses of all secondary endpoints except CHQ-PF28, PSI-4-SF and SNAP-IV ADHD will be based on both the mITT and ITT population but the analysis of CHQ-PF28, PSI-4-SF and SNAP-IV ADHD will be based on the ITT population only.

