7.8.6.1 Analysis of Key Secondary Efficacy Endpoint

The key secondary efficacy endpoint is the change from baseline (Visit 3) to Visit 6 in the Investigator CGI-S score.

This endpoint will be analyzed using Mixed-Effect Model for Repeated Measure (MMRM) for the mITT and ITT populations. The model includes treatment, visit, and interaction between treatment and visit as fixed factors, and baseline as covariate. The model parameters will be estimated using restricted maximum likelihood method with unstructured variance-covariance matrix and Kenward-Roger approximation to estimate denominator degrees of freedom. In case there is a convergence problem in the MMRM model with the unstructured variance covariance matrix, the first (co)variance structure which does not have convergence problem will be used for the analysis from the following ordered list: 1) Toeplitz [TOEP], 2) Autoregressive of Order 1 [AR(1)], and 3) Compound Symmetry [CS].

The least squares means of SPN-810 36 mg dose and placebo, the difference in the least squares mean (SPN-810 36 mg dose minus placebo), and the 2-sided 95% CI for the difference will be calculated (Table 14.2.2.1, Listing 16.2.2.2).

An example of SAS code is provided as follows.

```
ODS output DIFFS=DIF LSMEANS=LSMN;

PROC MIXED DATA=XXXX ;

CLASS trtp (ref='Placebo') usubjid visit;

MODEL Response = base trtp visit trtp*visit / DDFM=kr ;

REPEATED visit / SUBJECT=usubjid TYPE=UN ;

LSMEANS trtp*visit/PDIFF ALPHA=0.05;

RUN ;
```

Note: usubjid is subject ID, trtp is treatment variable, visit is the nominal study visit, and Response is respective endpoints.

In addition, the mean change from baseline by visit will be presented in Figure 14.2.4.1.

7.8.6.2 Analyses of Additional Secondary Efficacy Points

The following summaries and listings will be presented.

- 1. Investigator CGI-I score (continuous and binary) at Visits 4, 5, and 6 (Table 14.2.2.2.1 Table 2.2.2.2, Figure 14.2.3.1, and Listing 16.2.2.3)
- 2. PSI-4-SF score at visit 6 in total score and domains will be summarized in Table 14.2.2.4 (Listing 16.2.2.5.1 Listing 16.2.2.5.2).
 - a. Total Score
 - b. Parental Distress
 - c. Parent-Child Dysfunctional Interaction
 - d. Difficult Child
- 3. Caregiver CGI-I score (continuous and binary) by Visit (Table 14.2.2.5.1 Table 14.2.2.5.2, Figure 14.2.2.1, and Listing 16.2.2.3)
- 4. SNAP-IV ADHD scores at visit 6 will be summarized in Table 14.2.2.6 (Listing 16.2.2.6.1 Listing 16.2.2.6.2):

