 - a. Inattention ratings
 - b. Hyperactivity/Impulsivity ratings
 - c. Oppositional Defiant Disorder
 - d. Combined Scale ratings
- 5. Percentage of responders with 50% or more reduction in the frequency of IA from baseline to treatment period (Table 14.2.2.7)
- 6. Percentage of responders with 30% or more reduction in the frequency of IA from baseline to treatment period (Table 14.2.2.8)
- 1.

Scores of CGI-I (investigator and caregiver) will be analyzed using a Mixed-Effect Model for Repeated Measure (MMRM) similar to the key secondary outcome. CGI-S will be used as baseline covariate.

Scores for CHQ-PF28, PSI-4-SF, and SNAP-IV will be analyzed using analysis of covariance (ANCOVA) on the ITT population. The model includes treatment and baseline as fixed independent covariates and Visit 6 value as a response variable. The least squares mean of each treatment group, the difference in the least squares mean (SPN-810 36 mg dose minus placebo), and the 2-sided 95% CI for the difference will be obtained.

The SAS code for the ANCOVA will be:

```
PROC MIXED DATA=XXXX ;

CLASS trtp usubjid;

MODEL Response = base trtp / DDFM=kr ;

LSMEANS trtp t/PDIFF=control ('PLACEBO') ALPHA=0.05;

RUN ;
```

Where usubjid is subject ID, trtp is treatment variable and Response is CHQ-PF28, PSI-4-SF, and SNAP-IV at Visit 6.

The Percentage of responders defined as 50% or more reduction (and 30% or more reduction) in the frequency of IA from baseline to treatment period will be analyzed using the logistic regression model with treatment as explanatory variables. Odds ratio (36 mg Dose / Placebo), and 95% CI for the odds ratio and p-value will be presented. In addition, the number and percentage of responders will be tabulated.

```
An example of SAS code follows.

ODS OUTPUT OddsRatios=or /* ODDS RATIO AND 95% CL*/

LSMeans=lsm(keep=trtpn mu) /* PROB OF RESPONDERS */ ;

PROC LOGISTIC DATA=ef1 PLOTS=none ;

CLASS siteid trtpn / PARAM=glm ;

MODEL avalc(EVENT="Yes")=trtpn;

LSMEANS trtpn / PDIFF=controll('2') ILINK ;

RUN;
```

To control family-wise error rate at 0.05 for multiple endpoints, the key secondary endpoint and additional secondary endpoints will be ordered as follows: CGI-S, investigator CGI-I, CHQ-PF28, PSI-4-SF, caregiver CGI-I, SNAP-IV ADHD, Percentage of responders with 50% or more reduction in the frequency of IA, percentage of responders with 30% or more reduction in the frequency of IA. The testing will proceed in the following order.

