- 1. Test the null hypothesis H₀: There is no difference between the 36 mg dose SPN-810 and placebo will be performed with respect to CGI-S. If not rejected then the hypothesis will not be tested with respect to any additional secondary endpoint.
- If H₀ is rejected above, then proceed to test the same null hypothesis with respect to the 1st additional secondary endpoint (CGI-I). If not rejected then the hypothesis will not be tested with respect to any additional secondary endpoint after CGI-I.
- If H₀ is rejected above for CGI-I, then test of H₀ for the 2nd additional secondary endpoint (CHQ-PF28) will follow. If not rejected then the hypothesis testing will stop with respect to any subsequent additional secondary endpoint after CHQ-PF28. Otherwise, proceed

to test the same null hypothesis with respect to the 3rd additional secondary endpoint (PSI-4-SF).

The process will be repeated until all the secondary endpoints are gone through in the predefined order above in the same manner.

Subgroup (age, gender and race) analyses will be performed for the key secondary endpoint to explore the heterogeneity of the treatment effect across subgroups (Table 14.2.3.1.1-Table 14.2.3.1.3).

Supportive analyses will also be performed by summarizing the descriptive statistics for primary and secondary endpoints (Table 14.2.4.1 – Table 2.4.7).

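### The key secondary endpoint (CGI-S) is not conditional on the primary, and several secondary gates have no deciding population or no rule for multiple scores

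*Protocol*

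**What the plan says.** **Link to the primary.** Protocol 6.9.3 says: "If the null hypothesis for the primary analysis is not rejected, then no multiplicity adjustment will be done for the key secondary endpoint". Its next sentence starts the sequence of additional secondary endpoints once CGI-S is rejected and does not mention the primary.

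SAP 1 and Protocol 6.1 both give the SAP precedence on statistical methods. SAP 6.8 discusses the primary and key secondary only in relation to the dropped 18 mg arm, then says: "Multiplicity adjustment for the multiple endpoints with respect to additional secondary end points will be carried out in a fixed sequential gate-keeping approach". SAP 7.8.6.2 says: "To control family-wise error rate at 0.05 for multiple endpoints, the key secondary endpoint and additional secondary endpoints will be ordered as follows: CGI-S", followed by investigator CGI-I, CHQ-PF28, PSI-4-SF, caregiver CGI-I, SNAP-IV and the two responder rates. Step 1 tests CGI-S: "If not rejected then the hypothesis will not be tested with respect to any additional secondary endpoint". No condition precedes step 1.

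**Population.** For the primary, SAP 7.8.1 uses mITT and adds: "The analysis will be repeated for the ITT population, which follows the original primary efficacy analysis population definition". For CGI-S, SAP 7.8.6.1 says: "This endpoint will be analyzed using Mixed-Effect Model for Repeated Measure (MMRM) for the mITT and ITT populations". For the rest, SAP 7.8.6 says: "The analyses of all secondary endpoints except CHQ-PF28, PSI-4-SF and SNAP-IV ADHD will be based on both the mITT and ITT population"; the three excepted endpoints are ITT only. Protocol 6.9.2 says: "The Key Secondary endpoint will be analyzed using Mixed-Effect Model for Repeated Measure (MMRM) for the ITT population".

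**Scores per gate.** SAP 5.2.2 lists two summary scores for CHQ-PF28, three subscales for PSI-4-SF and four scores for SNAP-IV. SAP 7.8.6.2 adds a PSI-4-SF total. Each instrument is a single step in the testing order.

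**The concern.** In a fixed sequence that protects the trial's claims, the primary is the first gate. Here it is outside the sequence. The one current sentence on a failed primary does not stop testing: it says CGI-S needs no adjustment. The only wording that made secondary testing depend on primary success sits in the protocol's change log and has been superseded.

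A failed primary could thus be followed by a CGI-S result at p<0.05, and by every later endpoint it opens, reported under the SAP's statement of family-wise control. Separately, where a gate has two populations or several scores, the p-value that opens it could be chosen after the results are known.

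**Working it through.** **Inputs.** Two-sided alpha of 0.05 per test (SAP 6.1; Protocol 6.9.1 for the primary). The order and stopping rule come from SAP 7.8.6.2, and scores per gate from SAP 5.2.2. The documents give no correlation between endpoints or scores and no mITT-to-ITT ratio, so those below are assumptions.

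**Step 1: the SAP's own 0.05.** In a fixed sequence with one test per gate and all nulls true, an error requires the first gate to be falsely passed. Family-wise error is then the alpha of that gate, 0.05. This reproduces the SAP's figure, but only for the family it names (CGI-S onward) and only with one test per gate.

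**Step 2: primary plus ungated CGI-S, both nulls true.** If independent: 1 − 0.95² = 0.0975. For correlation ρ, the error is 1 − P(|Z₁| < 1.96, |Z₂| < 1.96) for a bivariate normal pair. Subtracting the primary's 5% gives the part where the primary fails and CGI-S rejects.

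| Assumed ρ | Error over the pair | Primary fails, CGI-S rejects |
|---|---|---|
| 0 | 9.75% | 4.75 points |
| 0.3 | 9.5% | 4.5 points |
| 0.5 | 9.1% | 4.1 points |
| 0.7 | 8.3% | 3.3 points |

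A gate on the primary removes the last column and returns the pair to 5%.

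**Step 3: two populations at one gate.** The gap affects CGI-S, both CGI-I endpoints and both responder endpoints. If either population could open the gate, and mITT is a fraction f of ITT, the two statistics correlate at about √f:

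| Assumed f | √f | Gate error |
|---|---|---|
| 0.95 | 0.975 | 6.0% |
| 0.90 | 0.949 | 6.5% |
| 0.80 | 0.894 | 7.1% |

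**Step 4: several scores at one gate.** These figures apply only if any one score suffices (no passage says so), that gate's nulls are true, and all earlier gates were passed on true effects. Scores are taken as equicorrelated. The SNAP-IV Combined score is modelled as the standardised sum of its two ADHD subscales (10,000,000 simulated draws).

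| Gate | ρ = 0.3 | ρ = 0.5 | ρ = 0.7 |
|---|---|---|---|
| CHQ-PF28, 2 scores | 9.5% | 9.1% | 8.3% |
| PSI-4-SF, 3 subscales | 13.6% | 12.5% | 10.9% |
| SNAP-IV, 4 scores | 14.5% | 13.0% | 11.1% |

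Adding the PSI-4-SF total as a standardised sum of the three subscales raises 12.5% to 12.9% at ρ = 0.5. If all scores must be significant, each gate stays at or below 5%.

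**The case against.** The strongest reply is that the protocol sentence does not govern. The SAP supersedes it and does not repeat it, and it may be a slip for the case where the primary is rejected. That is fair, but correcting the slip would not help: no passage in either document stops CGI-S from being tested after a failed primary. SAP 7.8.6.2 writes out the order and stopping rule, and the primary is in neither.

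It can also be said that no stated error rate is contradicted for the primary and CGI-S together. The SAP's 0.05 is claimed for the secondary endpoints only, and no text says CGI-S will be claimed after a failed primary. This stands as a description: the defect is a missing safeguard. The plan nonetheless attaches a family-wise claim to a sequence that a failed primary does not close.

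On population, Protocol 6.9.2 and 6.9.3 name ITT for the secondaries, and a reader might instead carry over the SAP's hierarchy for the primary (mITT first, ITT as repeat). These two readings give different answers for CGI-S, and the SAP chooses neither.

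On the multi-score gates, the any-score reading appears nowhere and an all-scores reading is not excluded. That is right. The figures in Steps 3 and 4 show what is possible under one reading and carry less weight than Step 2.

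**Conclusion.** The concern holds and should be fixed. As written, CGI-S can be tested at an unadjusted 0.05 after a failed primary. Under the global null this puts 8.3% to 9.75% error on the pair for correlations between 0.7 and 0, against 5% with a gate. The primary test's own error rate is not affected.

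The missing gate follows directly from the text. So do the absence of a deciding population for five endpoints and of a passing rule for three. The size of those last two gaps depends on how a gate would be read and on assumed mITT fractions and score correlations: 6.0% to 7.1% if either population may open a gate, and roughly 8% to 14.5% at a multi-score gate if any score may.

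**What to change.** - Delete the sentence in Protocol 6.9.3. State in SAP 6.8 and 7.8.6.2 that CGI-S is tested confirmatorily only if the primary test gives p<0.05 in its designated primary population, and that CGI-S and later p-values are otherwise nominal.
- Name one deciding population for each gate, with the other supportive. Reconcile this with Protocol 6.9.2 (ITT) and with CHQ-PF28, PSI-4-SF and SNAP-IV being ITT only.
- For those three instruments, either require every listed score to be significant or pre-specify one score before the next gate opens. Settle whether the PSI-4-SF total belongs to its gate.

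These are wording changes to the protocol and SAP, to be made before unblinding. They need the usual sponsor approval, and IRB approval if treated as affecting scientific quality (Protocol 7.2). Data collection, sample size and the primary test do not change. The price is that no confirmatory CGI-S claim is possible after a failed primary, and an all-scores rule makes the multi-score gates harder to pass.

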## 6.9.4 Sensitivity Analysis

In the presence of a high drop-out rate, performance of sensitivity analysis is crucial. The purpose of sensitivity analysis is to see whether different methods of handling missing data provide consistent and similar results for the primary efficacy analysis. To this end, two sensitivity analyses will be performed:

- 1. Multiple imputation under MAR using available data on the primary endpoint
- 2. Placebo- based imputation under MNAR

## 6.9.4.1 Multiple imputation under Missing at Random (MAR)

The multiple imputation (MI) method assumes that the missing data are missing at random (MAR), that is, the probability that an observation is missing may depend on the observed values but not the missing values. For example, if a subject's Diary values are available on Day 1 and Day 2 but missing on Day 3, then the missing value on Day 3 is related to the non-missing value on Day 1 and Day 2.

MI is implemented using the following three steps.

Supernus® Pharmaceuticals, Inc. 810P302

- 1) SAS PROC MI is applied with input dataset containing some missing values for all days during the titration and maintenance period to create 100 datasets. The data sets will include separate columns for the frequency of incidences during each day starting from baseline. The Markov Chain Monte Carlo (MCMC) method will be used to complete the missingness pattern to a monotone pattern separately by treatment arm. The monotone patterns will be achieved by applying sequential imputation based on Bayesian regression with the treatment arm included as a covariate. All copies contain identical values of the non-missing data items, but different values imputed for missing values.
- 2) For each of these MI data sets, the percent change will be computed as in the observed data set and the primary analysis based on the Wilcoxon rank-sum test will be conducted and asymptotic 95% confidence intervals will be constructed.
- 3) To produce a single confidence interval for each dose placebo comparison (e.g., Dose 1 versus placebo), PROC MIANALYZE will be used and Rubin's combination rules will be applied to the treatment effect estimates and associated asymptotic standard errors from the MI data sets (Rubin 1987). The treatment effect estimates will be defined as the midpoints of the asymptotic confidence intervals and the standard errors will be defined as the asymptotic standard errors (based on the width of the associated 95% confidence intervals) from the Hodges-Lehmann estimate of the individual datasets.

